9.1 PRIMARY EFFICACY PARAMETER

The primary efficacy parameter will be the change from baseline to Day 21 in MADRS total score for the mITT population. The MADRS total score is the sum of the 10 individual items. If more than 2 items are missing, then the total score will be set to missing. If there are multiple assessments of MADRS total score for the same nominal visit of a patient, only the last assessment will be used in the analysis.

The primary efficacy parameter will be analyzed using a mixed model for repeated measures (MMRM) with treatment group, pooled study center, visit, placebo responder status at Day 7, and treatment group-by-visit interaction as the fixed effects, and Day 0 MADRS total score, baseline MADRS total score, Day 0 MADRS total score-by-visit and baseline MADRS total score-by-visit interactions as covariates. An unstructured covariance matrix is used to model the covariance of change in scores within patients. The Kenward-Roger approximation will be used to estimate denominator degrees of freedom ([Kenward et al, 1997](#)). The analysis will be performed based on all post-randomization data using only the observed cases without imputation of missing values.

In the case that the MMRM model with unstructured covariance fails to converge with the default algorithm, then the Fisher scoring algorithm will be used to provide better initial values of the covariance parameters; if the model still does not converge, a simplified model without term for study center will be used to find the initial values of the covariance parameters. In the rare event that the model still does not converge after using those initial values, simplified covariance structures will be used to fit the model in the following order until the model converges: (1) ante-dependence, (2) heterogeneous autoregressive, (3) Toeplitz, and (4) compound symmetry.

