To assess the robustness of the primary MMRM results to the possible violation of the missing-at-random assumption, a sensitivity analysis using a pattern-mixture model based on non-future dependent missing value restrictions (Kenward et al, 2003) will be performed. The pattern for the pattern-mixture model will be defined by the patient's last visit with observed value. The observed MADRS total score at a visit is assumed to have a linear relationship with the patient's prior measurements. The missing values will be imputed under the assumption that the distribution of the missing observations differs from the observed only by a shift parameter value Δ . The dataset with missing values will be analyzed using the same model as the primary analysis for between-treatment group comparisons. The imputation of missing values and the analysis will be performed multiple times and the inference of this sensitivity analysis will be based on the combined estimates using the standard multiple imputation technique. The values for Δ will be selected as 0 to 8.

[figure not shown]

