Note that the two distributions only differ from a shift (Δ) parameter. When $\Delta = 0$, the missing value y_s in Pattern $s-1$ is imputed based on the distribution of all observed data up to Visit s , as a result, leading to missing at random (MAR) missingness. When $\Delta \neq 0$, (8) will introduce a scenario of MNAR. A similar idea was also presented in the recent publication “*The Prevention and Treatment of Missing Data in Clinical Trials*” by the National Academy Press. The selection of the plausible values for the shift parameter (Δ) is discussed in Section 3.

Note that per recommendation in Wang and Daniels (2011), only the observed data within the pattern is assumed to be multivariate normal. The observed data distribution can be expressed in terms of the marginal distribution of baseline measurements and the conditional distributions of postbaseline measurements given earlier measurements. Assuming that these distributions are normal, the linear regression of each observation on prior observations will yield least-squares estimates of model parameters that can be utilized for independent posterior draws of model parameters for observed data. The multiple imputation approach will be used to estimate the overall mean at the final time point.

2. Imputation Procedure

All the missing data will be imputed to create a complete dataset, then statistical analysis can be performed using appropriate techniques such as **MMRM**. The imputation **can accommodate MNAR missing data mechanisms**, based on the theory discussed in the above sections.

The model parameters for each dropout pattern, i.e., the mean, variance and proportions of observations in each pattern, are drawn from their posterior distributions prior to the imputation of missing data for a single imputation.

The details of imputation within a pattern, say Pattern t , are as the following:

Step 1. Impute the first missing value y_{t+1} for each patient in Pattern t ($t = 1, \dots, T-1$):

- a. Compute estimates of mixture probabilities $\lambda_{s-1,j}$ in (7) with $s = t+1$ given the posterior draw of proportions of observations in each pattern and the posterior draw of regression parameters for the observed data.

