- b. Draw a random integer from $\{s, \dots, T\}$ to index a component distribution on the right hand side of (6), using mixture probabilities obtained in a). Draw y_{t+1}^* from the identified component normal distribution. Impute the missing y_{t+1} as $\tilde{y}_{t+1} = y_{t+1}^* + \Delta$.

Step 2. Impute the rest of the missing values of $y_{t+2}, y_{t+3}, \dots, y_T$ for patients in Pattern t:

Starting with imputation for y_{t+2} , first, similar to Step 1, draw y_{t+2}^* from the normal mixture (6) based on the observed y_1, \dots, y_t and the already imputed \tilde{y}_{t+1} for the patient. Then the missing y_{t+2} is imputed as $\tilde{y}_{t+2} = y_{t+2}^* + \Delta$ with probability δ_{t+1} and as $\tilde{y}_{t+2} = y_{t+2}^*$ with probability $1 - \delta_{t+1}$, where the mixture probability $\delta_{t+1} = \omega_{t+1,t+1}$ is obtained from (4) given the posterior draw of proportions of observations in each pattern and the posterior draw of regression parameters for the observed data.

Missing values of y_{t+3} through y_T can be imputed similarly as y_{t+2} .

To summarize, the imputations of y_{t+1} through y_T is done recursively within each Pattern t (for all $t = 1, \dots, T - 1$) to create a complete dataset after imputation is done for all patterns with missing values.

The above imputation procedure is applied to all subjects in each missing data pattern to create a single imputed data set. Repeating the process of drawing parameters from the posterior distribution and imputing missing data given the posterior draw m times will yield m imputed data sets. The observed or imputed values at the final data point are averaged to obtain the overall mean estimate for each imputed data set, and the multiple imputation estimate is obtained by averaging the estimates across m imputations.

In this sensitivity analysis, m is set to equal to 20. The value of m is discussed in the context of imputation efficiency in standard multiple imputation theory (Rubin, 1987, p. 114), and $m = 20$ would provide at least 96% of relative efficiency as compared with using an large number of imputations (SAS/STAT User's Guide, p. 3796).

3. Determination of the Shift Parameter Values

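### As written, the pattern-mixture imputation has no treatment term, so its shift-0 run does not make the missing-at-random assumption of the primary MMRM; the effect is small and its direction depends on the visit profile

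*SAP*

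**What the plan says.** SAP 9.1 plans a pattern-mixture sensitivity analysis to test the primary MMRM against departures from missing at random (MAR). Patterns are defined by the last visit with an observed value. The imputation model is described in one sentence: "The observed MADRS total score at a visit is assumed to have a linear relationship with the" patient's earlier scores. Protocol 9.7.5.1 gives the same description.

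Appendix II gives the detail:

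- Every conditional density conditions on earlier scores and dropout pattern only.
- On estimation: "the linear regression of each observation on prior observations will yield least-squares estimates of model parameters".
- On the unit of the posterior draws: "The model parameters for each dropout pattern, i.e., the mean, variance and proportions of observations in each pattern".
- On coverage: "The above imputation procedure is applied to all subjects in each missing data pattern to create a single imputed data set".
- A shift of zero is described as "leading to missing at random (MAR) missingness". According to 9.1, the shift values "will be selected as 0 to 8".

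The primary MMRM in 9.1 is richer. It has treatment group, pooled center, visit, responder status and "treatment group-by-visit interaction as the fixed effects", plus Day 0 and baseline scores with their visit interactions. The imputed data sets are analyzed with that same model.

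The history of changes (SAP 2.0, entry for Appendix II) records that the SAS code was moved to a separate document.

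**The concern.** An imputation model that leaves out a term of the analysis model can distort the estimate of that term. If dropouts from both arms are imputed from one regression on prior scores, their imputed Day 21 values carry only the part of the treatment effect already visible in those scores. The rest of the arm difference is lost or, if the early effect was larger than the late one, overstated.

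The shift-0 run is then MAR given prior scores, not MAR given prior scores and treatment. A reader who follows the series from 0 to 8 would attribute any departure from the primary estimate to the shift, when part of it is already present at shift 0. At stake is the interpretation of the MNAR analysis of the primary endpoint. The primary estimate itself is unaffected.

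**Working it through.** **Inputs.** SD 8.7, correlation 0.5, 230 per arm, and dropout of 10% in the randomized period plus 5% in the lead-in, with less than 5% overall observed (SAP 13.0). Six post-randomization visits: Days 8, 11, 14, 15, 18 and 21 (SAP Table 15.1–2). The difference of 3.25 is stated for the initial 700-patient calculation; the current text does not restate it for the re-estimate, so it is an assumption here. The visit profiles and the even spread of dropout over visits are also assumptions.

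**The plan's own figure.** A two-sample approximation gives n = 2(1.960 + 1.282)² × 8.7² / 3.25² = 151 per arm. Dividing by 0.85 gives 178 per arm, 356 in total, against the stated 360. So 3.25 is consistent with the re-estimate.

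**Which dropout rate applies.** Lead-in dropouts receive no randomized dose and fall outside the mITT population (SAP 5.3). The planned rate for this analysis is therefore 10%, not 15%; the observed overall rate is below 5%.

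**Closed form.** Let e be the arm differences at the visits observed before dropout and e₆ the difference at Day 21. With 1:1 allocation, pooling arms gives covariance V = Σ + ee′/4 among the observed visits and c = cov + e·e₆/4 with Day 21. The arm difference carried into the imputed values is c′V⁻¹e, and the gap is e₆ − c′V⁻¹e.

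For a constant effect d with k observed visits this reduces to gap = d·a/(a + k·b), where a = 0.5 × 8.7² = 37.845 and b = 37.845 + 3.25²/4 = 40.486:

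- k = 1: 3.25 × 37.845 / 78.331 = 1.57
- k = 5: 3.25 × 37.845 / 240.275 = 0.51
- mean over k = 1 to 5: (1.57 + 1.04 + 0.77 + 0.62 + 0.51)/5 = 0.90

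Multiplying by the fraction missing gives 0.90 × 0.05 = 0.045 points at 5% and 0.09 at 10%. At 5%, correlations of 0.3 and 0.8 give 0.073 and 0.015.

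For an effect growing over visits (0.5, 1, 1.5, 2, 2.6, 3.25) the mean gap is 2.47, giving 0.124 at 5% and 0.247 at 10%. For a steeply fading effect (5, 4, 3, 2.5, 2, 1) it is −1.68, giving −0.084 and −0.168. With no true effect it is zero.

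**Simulation.** Sequential-regression imputation at shift 0, 20 imputations, dropout depending on the last score, 300 replicates. The loss is the Day 21 difference with treatment in the regression minus that without it:

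| Profile | 5% dropout | 10% dropout |
|---|---|---|
| Constant 3.25 | 0.04 | 0.08 |
| Growing to 3.25 | 0.11 | 0.22 |
| Fading from 5 to 1 | −0.08 | −0.14 |

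In the constant case at 5%, the estimate with treatment was 3.28 against 3.27 in the full data; without treatment it was 3.23. A separate simulation of 1,500 trials per setting gave losses at 5% of 0.04 (3.22 against 3.18, constant) and 0.12 (3.27 against 3.15, growing).

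**Scale.** The standard error is about 8.7 × √(2/230) = 0.81. So 0.04 to 0.12 is about 5% to 15% of a standard error, and 0.22 is about 27%.

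**Limits.** The re-derivation compared Day 21 means with patterns pooled and without baseline as a predictor. The full non-future-dependent mixture followed by the MMRM was not run.

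**The case against.** The strongest reply is that the point rests on silence. Appendix II is generic, single-sample theory that ends in an overall mean, yet 9.1 requires a comparison between treatment groups. Some step involving arm must therefore exist, and running the template by arm is a reasonable reading. The statement about all subjects in a pattern can describe coverage and not pooling, and the code may settle the matter. This stands in part: the SAP does not say that arm is excluded, and a reader who infers that it is goes beyond the text. But a programmer following the written model would omit arm, and the SAP gives no means of telling which was done.

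A reader might also infer that shift 0 is always pulled toward no difference. The documents do not support that. Protocol 7.0 and 9.4.6 describe single-dose effects within a day that last about a week or longer, and the Day 21 target lies 7 days after the second randomized dose. A fading profile cannot be excluded, and in the steeply fading case above the estimate moved away from zero.

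It is also tempting to quote losses at 15% dropout, but SAP 13.0 places 5 of those percentage points in the lead-in.

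Finally, no passage requires shift 0 to reproduce the MMRM estimate. That is true. But the analysis is meant to test that MMRM against violation of MAR, so a zero-shift run under a different MAR assumption is a poor reference point.

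**Conclusion.** The point holds as a small specification gap. Followed as written, the imputation makes a MAR assumption different from that of the primary MMRM, and the shift series carries that mismatch throughout.

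Under the assumed profiles, with correlation 0.5 and dropout spread evenly over visits, the bias is about 0.04 to 0.12 points at 5% dropout. At the planned 10% it is about 0.08 to 0.22 in simulation, and up to 0.25 in closed form. Its sign depends on how the effect develops up to Day 21. Against a standard error near 0.8 it would seldom change a conclusion, least of all at the reported dropout below 5%. If the separate code already runs by arm or includes treatment, only the wording of the SAP needs correction.

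**What to change.** State in SAP 9.1 and Appendix II that the imputation regression at each visit includes treatment group, or is fitted separately by arm, in addition to all prior MADRS scores including baseline. Where dropout patterns are too sparse, estimate the treatment term in common across patterns. This matters because fewer than 5% of 460 is fewer than 23 dropouts; spread evenly over five dropout patterns (an assumption), that is under five patients each. Adding the Day 0 score and responder status is optional where they can be estimated.

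Add a check that the shift-0 estimate agrees with the primary MMRM up to Monte Carlo error, and confirm that the separate programming document matches the amended text.

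The cost is a few lines of SAP wording, a change to the imputation model if the code does not already contain it, and attention to estimability in sparse patterns. No new data are needed.

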9.2 KEY SECONDARY EFFICACY PARAMETERS

[figure not shown]
There are 3 key secondary efficacy parameters as listed below:

[figure not shown]
1. Change from baseline to Day 8 (1 Day after the first randomized treatment) in MADRS total score for mITT population
2. Change from baseline to Day 21 in MADRS total score for the placebo non-responders of mITT population
3. Change from baseline to Day 8 in MADRS total score for the placebo non-responders of mITT population

The key secondary parameters will be analyzed using the same MMRM model as for the primary efficacy parameter, except the placebo responder status at Day 7 will be excluded for the analyses of the 2nd and 3rd key secondary efficacy parameters listed above. A sequential testing procedure will be used to control the overall type I error rate at 5% for the comparisons of between-treatment difference of multiple secondary efficacy parameters in the order listed above. Specifically, the change from baseline to Day 8 in MADRS total score for the mITT population will be tested first at the significance level of 0.05. If the between-treatment comparison is statistically significant, then the analysis of 2nd and 3rd key efficacy parameters for the placebo non-responders will be performed at the same significance level sequentially as long as the treatment effect is statistically significant in the preceding testing.

Plots of fitted (least squares) mean values and their standard errors based on the MMRM model for the change in MADRS total score will be presented by treatment group and by visit.

REDACTED

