The primary efficacy parameter will be the change from baseline in MADRS total score at end of study. The primary analysis will be performed using a mixed-effects model for repeated measures (MMRM) with terms for treatment, pooled study center, visit, and treatment-by-visit interaction as the fixed effects, and baseline MADRS total score, baseline MADRS total score-by-visit as covariates. The key secondary efficacy parameter, change from baseline in MADRS total score 1 day after randomized treatment will be analyzed using the same MMRM model as was used for the primary efficacy parameter. An unstructured covariance matrix will be used to model the covariance of within-patient scores. Baseline will be defined as the last measurement prior to the first dose of double-blind treatment. To control the overall type I error rate for both the primary and key secondary endpoint, a sequential testing procedure will be implemented.

All safety parameters will be analyzed using descriptive statistics. Safety analyses will be based on the Safety Population, defined as all randomized patients who receive at least 1 dose of randomized treatment. Efficacy analyses will be based on the modified Intent-to-Treat (mITT) Population, defined as all patients who are randomized and receive at least 1 dose of treatment and have at least 1 postrandomization assessment of the MADRS total score.

3.0		I ABI	LE OF CO	DNIENIS	
1.0	TITLE	PAGE			1
2.0	SYNO	PSIS AN	D SCHEDU	JLE OF EVALUATIONS	2
3.0	TABL				
	3.1	LIST C	F FIGURE	S	9
4.0	LIST (OF ABBR	EVIATION	IS	10
5.0	ETHIC	CAL CON	ISIDERATI	ONS	12
	5.1			w Board and Independent Ethics Committee	
	5.2			the Study	
	5.3	Patient	Information	and Informed Consent	12
6.0	INVES	STIGATO	ORS AND S	TUDY ADMINISTRATIVE STRUCTURE	13
7.0	INTRO	DUCTIO	ON		14
8.0	STUD	Y OBJEC	CTIVES		18
9.0	INVES	STIGATIO	ONAL PLA	N	20
7.0	9.1			gn and Plan: Description	
		9.1.1		Period	
		9.1.2		ind Treatment Period	
		9.1.3		llow-up Period	
	9.2			y Design, Including the Choice of Control Groups	
	9.3			Population	
		9.3.1		Criteria	
		9.3.2		Criteria	
		9.3.3		of Patients from Therapy or Assessment	
	9.4	9.3.4		placement Procedures	
	7.4	9.4.1		nd Antidepressant Therapy	
		9.4.2		ts Administered	
		9.4.3		f Investigational Products	
		9.4.4		of Investigational Products	
		9.4.5		f Assigning Patients to Treatment Groups	
		9.4.6		of Dosages in the Study	
		9.4.7		and Timing of Dose for Each Patient	
			9.4.7.1	Screening Period	31

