9.7.5.2 Key Secondary Efficacy Parameter

The key secondary efficacy parameter will be the change from baseline to 1 day after the first dose of treatment in MADRS total score. This parameter will be analyzed using the same MMRM as will be used for the primary efficacy parameter. The treatment difference for rapastinel versus placebo will be estimated and reported along with the corresponding 95% CI and nominal p-value.

A sequential testing procedure will be used to control the overall type I error rate at 5% for the primary and secondary efficacy parameters.

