9.0 EFFICACY ANALYSES

All efficacy analyses will be based on the mITT Population, unless stated otherwise. The baseline for each specific efficacy endpoint is defined as the last measurement prior to the first dose of randomized treatment. The Day 0 measure for each specific efficacy endpoint is defined as the last measurement prior to the first dose of double-blind IP in the placebo lead-in period. The analyses for the placebo lead-in period will be presented for all patients combined and separately for the placebo responders vs. non-responders using the Enrolled Population. All statistical hypothesis tests will be performed at the 2-sided 5% significance level for main effects. All confidence intervals (CIs) will be 2-sided 95% CIs, unless stated otherwise.

For efficacy analyses in which study center is a factor, a *small center* will be defined as a center with less than 2 placebo non-responder patients in at least 1 treatment group in the mITT Population. Small centers will be pooled to form pseudo-centers so that each treatment group includes at least 2 placebo non-responder patients within the center for the mITT population. Pooling will be done using the following algorithm:

Based on the number of placebo non-responder mITT patients, small centers will be ordered from the largest to the smallest, and centers of the same size will be ordered from the largest center number to the smallest center number. The pooling process starts with the largest small center from the top, which will be pooled with the smallest from the bottom until a non-small center is formed. The process will be repeated using the small centers left out after the first pass. If any centers are left out at the end of the process, they will be pooled with the smallest pseudo-center. If there is more than 1 smallest pseudo-center, the pseudo-center with the smallest center number will be selected. In case the pseudo-center formed by pooling all small centers is still a small center, it will be pooled with the smallest non-small center. If there is more than 1 smallest non-small center, the one with the smallest center number will be selected.

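### SAP 9.2 tests Day 8 at 0.05 with no condition on the Day 21 primary, so the protocol's 5% overall type I error is not kept

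*SAP*

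**What the plan says.** **Protocol.** The synopsis (section 2.0) gives the scope: "To control the overall type I error rate for both the primary and key secondary endpoint, a sequential testing procedure will be implemented". Section 9.7.5.2 adds the level, saying the procedure is to "control the overall type I error rate at 5% for the primary and secondary efficacy parameters". Neither place states the order of tests or a gate.

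**SAP.** Section 9.0 sets the level of every test: "All statistical hypothesis tests will be performed at the 2-sided 5% significance level for main effects". Section 9.1 defines the primary: "The primary efficacy parameter will be the change from baseline to Day 21 in MADRS total score for the mITT population". It contains no multiplicity rule. Section 9.2 lists three key secondaries: Day 8 in the mITT population, Day 21 in placebo non-responders, and Day 8 in placebo non-responders. It applies the 5% control to comparisons "of multiple secondary efficacy parameters in the order listed above", a list that does not contain the primary. The first of the three "for the mITT population will be tested first at the significance level of 0.05", and the second and third each follow only if the preceding test is significant. The SAP's history of changes describes the procedure in the same way, as multiplicity control for the secondary endpoints.

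**The concern.** The two documents describe different families. The protocol's family contains the primary and the secondary; the SAP's contains the secondaries only. A statistician who follows SAP 9.2 literally runs two unlinked 0.05 tests, Day 21 and Day 8, both in the mITT population.

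The difference matters if Day 21 fails and Day 8 succeeds, which is a foreseeable result here:

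- The protocol's introduction and dose-selection section describe single-dose effects that appear within a day and last about a week. The SAP's visit windows place Day 21 seven days after the second randomized dose.
- Day 8 was the time point of the previous primary endpoint, replaced after regulatory feedback. Without a gate it keeps a full 0.05 route to a formal claim when the new primary fails.
- A Day 8 success then opens Day 21 in placebo non-responders, which is the failed primary question asked again in a subset.

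The protocol says the study is meant to support an application for approval, so it matters which claims are covered by the stated error rate.

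**Working it through.** **Inputs from the documents**

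- Overall type I error promised for primary plus secondary: 5% (protocol 9.7.5.2).
- Level of each test: two-sided 0.05, critical value 1.96 (SAP 9.0).
- Correlation between repeated measures: 0.5 (SAP 13.0, protocol 9.7.9).
- Difference 3.25, SD 8.7, 230 per arm (SAP 13.0).

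**Assumptions**

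- The 0.5 is a planning value for repeated measures. The documents give no correlation for the Day 8 and Day 21 test statistics, so 0.5 is borrowed and a range is shown.
- The share of placebo non-responders is not given. Values from 60% to 80% are assumed.

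**Step 1. The planning figures reproduce.** 350 per arm with SD 10 and difference 3.25 gives power 0.990, against the stated 99%. SD 8.7 and 90% power need 151 per arm; 151 / 0.85 = 178 per arm, 356 in total, against the stated 360. The 5% overall error does not reproduce, as follows.

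**Step 2. No effect at any visit.** Under the SAP rule the later secondaries are reached only after Day 8 is significant, so the family makes an error exactly when Day 21 or Day 8 in the mITT population is significant:

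FWER = 1 − P(|Z₂₁| < 1.96 and |Z₈| < 1.96), with (Z₂₁, Z₈) bivariate normal.

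| Correlation | FWER |
|---|---|
| 0 | 1 − 0.95² = 0.0975 |
| 0.3 | 0.0951 |
| 0.5 | 0.0907 |
| 0.7 | 0.0835 |
| 0.8 | 0.0781 |
| 0.9 | 0.0704 |

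The bound is 0.05 + 0.05 = 0.10, and 5% is reached only at correlation 1. A simulation of all four tests (1,000,000 trials per scenario) gave 0.090 to 0.091 at correlation 0.5.

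**Step 3. False Day 8 claim after a failed primary.** P(Day 8 significant, Day 21 not) = FWER − 0.05 = 0.0907 − 0.05 = 0.0407 at correlation 0.5.

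**Step 4. Real effect at Day 8, none at Day 21.** The false claims are now Day 21 in the mITT population and Day 21 in non-responders. The two statistics at the same visit correlate at √(non-responder share). If Day 8 is certain to be significant, the Step 2 formula gives:

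| Share | Correlation | Error |
|---|---|---|
| 60% | 0.775 | 0.0796 |
| 75% | 0.866 | 0.0734 |
| 80% | 0.894 | 0.0709 |

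These are upper limits, because Day 8 is not certain to succeed. The planning figures imply SE = 8.7 × √(2/230) = 0.811 and mean Z = 3.25 / 0.811 = 4.0. At that mean Z, with correlation 0.5 between visits, simulation gives 7.9% at 60% and 7.0% at 80%. With Day 8 power of only 80% the range is 7.3% to 6.6%, and with 50% it is 6.5% to 6.0%.

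**Step 5. With the gate.** If Day 8 is tested only after Day 21 is significant at 0.05, and the others follow in order, no claim can precede a significant primary and the error is at most 5% by construction. Simulation gave 0.0497 to 0.0503 in every scenario.

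**The case against.** The strongest reply is that the gate is intended and simply not repeated. In a section on key secondaries, being tested first can mean first among the three. SAP 3.0 presents the SAP as a more detailed version of the protocol, and SAP 16.0 declares no change beyond two added analyses that have nothing to do with multiplicity. Read with the protocol, the primary might be taken to come first. The SAP also rests on a Restricted Access Addendum that is not among the documents, and the order could be stated there.

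Intent is indeed uncertain, and so is the content of the addendum. Neither supplies the missing condition. The protocol gives no order to fall back on, and the SAP, the only document here with an operative rule, states a narrower scope in both section 9.2 and its history of changes. If the addendum does contain the gate, the SAP disagrees with it and still needs correcting.

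Two further points stand as limits on the claim. The primary test keeps its own 5%, and the secondary family alone is also held at 5% (0.046 to 0.050 in simulation), so the SAP meets its own narrower statement. The size of the excess depends on a borrowed correlation, although some excess remains at every value below 1.

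**Conclusion.** The concern holds. As written, SAP 9.2 does not deliver the overall 5% that the protocol promises for the primary and secondary parameters together. With no effect at either visit, the familywise error is 9.1% at an assumed correlation of 0.5, and between 9.75% and 7.0% for correlations from 0 to 0.9. The chance of a false Day 8 claim alongside a failed primary is 4.1% at 0.5. If the drug works at Day 8 only, the error through the non-responder route is about 7.0% to 7.9%, assuming 80% to 60% non-responders and a Day 8 effect of the planned size; it is smaller if the Day 8 effect is weaker. The validity of the primary test itself is not in question. The rule needs correcting because it permits formal claims after a failed primary in a study meant to support approval.

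**What to change.** In SAP 9.2, replace the opening of the sequence with one that starts at the primary:

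1. Day 21, mITT, at two-sided 0.05.
2. Day 8, mITT, only if 1 is significant.
3. Day 21, placebo non-responders, only if 2 is significant.
4. Day 8, placebo non-responders, only if 3 is significant.

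State that the 5% covers all four tests and that p-values after the first non-significant result are nominal. Put the same order in protocol 9.7.5.2, which names only one key secondary where the SAP has three, and check that the addendum agrees. The change must be dated before unblinding, since a gate chosen with results in hand carries no weight.

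The cost is a sentence or so in each document, with no alpha split and no change in sample size. What is given up is a formal Day 8 claim when the primary fails, and the protocol's statement of overall control already leaves no room for an unadjusted one.
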